4.5 History of cardiac surgical procedures and catheter interventions

This will be described per study group for the FAS populations.

4.6 Efficacy Analyses

4.6.1 Primary Efficacy Analysis

Primary efficacy analysis, test between FAV vs no-FAV regarding transplantation-free survival from fetal diagnosis to 2 years postnatal age, having a biventricular circulation without pulmonary hypertension at that time, will be performed using logistic regression adjusted for confounders identified according to the section General Methodology above. OR with 95% CI will be presented. The primary analysis will be performed on FAS_{ENR} population and will compare FAV 1+2 versus no-FAV 1+2. This analysis will be included in the evaluation of the confirmatory tests. Complementary analyses will be performed on FAS_{BIRTH}, PP_{ENR}, PP_{BIRTH} populations, and on all populations comparing FAV 1 with no–FAV 1 and FAV 1 vs no-FAV 1+2.

Sensitivity analyses will be performed using Fisher's exact test comparing the FAV group with the matched no-FAV group obtained applying propensity score matching according to the description in General Methodology above, both on FAS and PP populations.

Vertical bar charts will be presented for graphical purpose.

4.6.2 Secondary Efficacy Analyses

Secondary variables will be analysed according to described methods in General Methodology above.

STATISTISKA KONSULTGRUPPEN	Statisti	cal Analysis Plan
Effect of fetal aortic valvuloplasty on outcomes	Protocol No):
	Version:	

1.0 Page 24 of 26

4.6.3 Subgroup Analyses

Descriptive data on primary and secondary outcomes will be performed on following subgroups for FAV 1+2 vs no-FAV 1+2, FASENR and FASBIRTH populations:

- Subgroup 1: Fetuses with diagnosis of fetal aortic stenosis that undergo technically . successful FAV and additional fetal cardiac intervention(s) such as atrial septal balloon dilatation or stent placement.
- Subgroup 2 (part of the High-risk population): Fetuses with diagnosis of fetal aortic stenosis and hydrops.
- Subgroup 3 (equals to High-risk population): Fetuses with diagnosis of fetal aortic stenosis, severe mitral regurgitation and left atrial enlargement with or without restrictive or intact atrial communication and with or without hydrops.

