2 STUDY POPULATIONS

2.1 Definition of Study Populations

2.1.1 Full Analysis Set for All Enrolled

Fetuses with severe MR and severe LA enlargement and/or intact or highly restrictive interatrial communication and/or cases with hydrops present at inclusion are all high-risk cases regarding survival, but may have a rather good prognosis if they survive the first critical period. It is likely they will be overrepresented in the FAV group to such a degree that it will be difficult to control for through propensity score matching. Therefore this subpopulation will be excluded from the full analysis set and analysed separately. Fetuses developing any of these conditions after inclusion will not be excluded from the full analysis set.

All enrolled fetuses that have satisfied inclusion/exclusion criteria and belong to FAV 1+2 and no-FAV 1+2 groups and not listed as belonging to the high-risk population described above will be included in the Full Analysis Set enrolled (FAS_{ENR}) population. Infants wrongly included in the study (not fulfilling all inclusion or fulfilling any of the exclusion criteria) will not be part of the FAS_{ENR} population, but will be described in the safety analyses. As detailed under 1.3.2, also subjects with exclusion criteria present at inclusion but diagnosed only after birth will be retrospectively excluded from the FAS_{ENR} population.

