2.1.2 Full Analysis Set for Live Births Intended for Postnatal Treatment

All enrolled fetuses that have satisfied inclusion/exclusion criteria and belong to FAV 1+2 and no-FAV 1+2 groups and not listed as the high-risk population above that also are live at birth will be included in the Full Analysis Set at birth (FAS_{BIRTH}) population. Infants wrongly included in the study will not be part of the FAS_{BIRTH} population, but will be described in the safety analyses.

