2.1.3 Per-Protocol Population for All Enrolled

All enrolled fetuses with no major protocol violations will be included in the Per Protocol enrolled (PP_{ENR}) population. The final decisions regarding the PP_{ENR} population will be taken at the Clean File meeting before the database lock.

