2.1.5 High-Risk Population

The high-risk population will include all subjects with any of the following conditions at inclusion: Severe MR and severe LA enlargement and/or intact or highly restrictive inter-atrial communication and/or hydrops. Fetuses developing any of these conditions after inclusion will not be analysed as belonging to the high-risk population.

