7.1 Listing of Tables

Statistical Analysis Plan

Protocol: Effect of fetal aortic valvuloplasty on outcomes

Protocol No:

2.1.4	Adjusted Analysis of Primary Efficacy Variable (PP At Birth Population)
2.2.1	Sensitivity Analysis of Primary Efficacy Variable (FAS Enrolled Population)
2.2.2	Sensitivity Analysis of Primary Efficacy Variable (FAS At Birth Population)
2.2.3	Sensitivity Analysis of Primary Efficacy Variable (PP Enrolled Population)
2.2.4	Sensitivity Analysis of Primary Efficacy Variable (PP At Birth Population)
2.3.1	Adjusted Analysis of Secondary Efficacy Variables (FAS Enrolled Population)
2.3.2	Adjusted Analysis of Secondary Efficacy Variables (FAS At Birth Population)
2.3.3	Adjusted Analysis of Secondary Efficacy Variables (PP Enrolled Population)
2.3.4	Adjusted Analysis of Secondary Efficacy Variables (PP At Birth Population)
2.4.1.1	Descriptive Data on Primary and Secondary Variables (FAS Enrolled Population – Subgroup 1)
2.4.1.2	Descriptive Data on Primary and Secondary Variables (FAS Enrolled Population – Subgroup 2)
2.4.1.3	Descriptive Data on Primary and Secondary Variables (FAS Enrolled Population – Subgroup 3)
2.4.2.1	Descriptive Data on Primary and Secondary Variables (FAS At Birth Population – Subgroup 1)
2.4.2.2	Descriptive Data on Primary and Secondary Variables (FAS At Birth Population – Subgroup 2)
2.4.2.3	Descriptive Data on Primary and Secondary Variables (FAS At Birth Population – Subgroup 3)
3.1	Intervention and Technical Details (Safety Population)
3.2.1	Infants' Complications and Reasons for Death (Safety Population)
3.2.2	Maternal Complications (Safety Population)
3.2.3	Infants Diagnoses at Discharge (Safety Population)
3.2.4	Infants Cardiac Surgical Interventions during the Study (Safety Population)
3.3.x	Mixed Models for Repeated Data Performed on ECHO Variables (Safety Population)

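### The SAP removes high-risk fetuses from both full analysis sets, then specifies their only dedicated efficacy tables on those same sets, and does not say whether the per-protocol sets exclude them

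*SAP*

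**What the plan says.** SAP 2.1.1 describes fetuses with poor early prognosis, expects them to be more common in the FAV group than propensity matching can handle, and concludes: "Therefore this subpopulation will be excluded from the full analysis set and analysed separately". Section 2.1.2 repeats the exclusion for live births; only fetuses "not listed as the high-risk population above that also are live at birth will be included in the Full Analysis Set at birth" population.

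Section 2.1.5 defines the group: "The high-risk population will include all subjects with any of the following conditions at inclusion", the conditions being "Severe MR and severe LA enlargement and/or intact or highly restrictive inter-atrial communication and/or hydrops". Fetuses that develop a condition later do not count as high-risk and stay in the FAS.

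Section 4.6.3 plans descriptive primary and secondary outcomes for the "following subgroups for FAV 1+2 vs no-FAV 1+2, FASENR and FASBIRTH populations". Subgroup 2 is fetuses with hydrops, labelled as part of the High-risk population. The third reads: "Subgroup 3 (equals to High-risk population): Fetuses with diagnosis of fetal aortic stenosis, severe mitral regurgitation and left atrial enlargement", with or without septal restriction and hydrops. The table list follows suit; Table 2.4.1.3, for example, is "Descriptive Data on Primary and Secondary Variables (FAS Enrolled Population – Subgroup 3").

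The per-protocol set is defined in 2.1.3 as follows: "All enrolled fetuses with no major protocol violations will be included in the Per Protocol enrolled" population. Section 2.1.4 is worded alike for live births intended for treatment. Neither mentions the high-risk exclusion.

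The protocol (text after Exclusion criteria, and subgroup c under Data analysis and statistical support) treats cases with severe MR and LA enlargement as eligible but to be analysed apart.

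**The concern.** The case for leaving these fetuses out of the main analysis rests on reporting them separately. If the separate tables are specified on sets that exclude them, the plan contains no executable efficacy summary for a group that it expects to be at high risk of death and concentrated in the FAV arm. Someone would then have to decide which fetuses belong in which table when the tables are programmed, possibly with outcomes already known.

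The per-protocol wording raises a second issue. The primary variable is analysed on PP_ENR and PP_BIRTH, and 4.6.1 applies propensity matching there as well. If high-risk fetuses are in PP but not in FAS, a difference between FAS and PP results could reflect case mix rather than adherence. Severe MR, LA size, septal restriction and hydrops are not among the potential confounders listed in 3.1, although 4.1 allows others to be added.

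**Working it through.** The plan gives no figure on this point, so the check is set logic on the written definitions.

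**Step 1: the intended sets.** Let H be the fetuses meeting 2.1.5 at inclusion. By 2.1.1, FAS_ENR ∩ H = ∅. By 2.1.2, FAS_BIRTH ∩ H = ∅.

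**Step 2: the subgroups as labelled.** Subgroup 3 = H and Subgroup 2 ⊂ H. Restricted to either FAS set, both are empty. There are 3 subgroups × 2 populations = 6 subgroup tables. The two for Subgroup 2 and the two for Subgroup 3 are affected, so 4 of 6 hold none of their intended fetuses. No other efficacy table is titled for the High-risk population, and 4.2 does not list it among the sets to be summarised.

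**Step 3: the subgroups as described.** Some fetuses can be traced through the literal wording instead of the labels:

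| Status | In H (2.1.5) | In FAS_ENR | Fits Subgroup 2 text | Fits Subgroup 3 text | Appears in a subgroup 2 or 3 table |
|---|---|---|---|---|---|
| Severe MR and severe LA enlargement at inclusion | yes | no | no | yes | no |
| Hydrops alone at inclusion | yes | no | yes | no | no |
| Intact or highly restrictive septum alone at inclusion | yes | no | no | no | no |
| Hydrops only after inclusion | no | yes | yes, if timing is ignored | no | possibly |
| Severe MR, LA enlargement less than severe, at inclusion | no | yes | no | yes | yes |

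Any fetus that does reach these tables is therefore one that 2.1.5 says is not high-risk. The third row shows a separate gap: that fetus fits neither subgroup description, so changing the population label alone would still leave it without a dedicated table. This reads the list in 2.1.5 as three alternatives, as its introductory words indicate.

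**Step 4: the per-protocol sets.** PP_ENR = enrolled fetuses minus major violations. The protocol makes these cases eligible, so being high-risk is not in itself a violation. On the text, PP_ENR ∩ H need not be empty, and PP_ENR is not necessarily a subset of FAS_ENR. The same holds for PP_BIRTH and FAS_BIRTH.

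**Step 5: what is not touched.** The confirmatory sequence in 4.1 and the primary analysis in 4.6.1 use FAS_ENR for FAV 1+2 against no-FAV 1+2. None of the steps above changes who is in FAS_ENR.

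**The case against.** The subgroup analyses are descriptive, with no test attached. The intent is clear from 2.1.1, 2.1.5, the Subgroup 3 label and the protocol, and a programmer who met an empty table would probably ask. These fetuses also stay in the safety population, which covers deaths, discharge diagnoses and cardiac procedures. All of this stands and limits the weight of the point. It does not make the tables executable as written, and the safety tables are split by treatment group, not by risk.

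On the per-protocol sets, the title of Table 1.2 ties exclusions from PP to the FAS Enrolled population, which suggests that PP was meant to be nested in FAS_ENR. Figures 5 and 6, which I could not see, may show the same, and final PP decisions are left to the Clean File meeting. The PP analyses are complementary only. So readmission is what the text permits, not something established.

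Three stronger readings are tempting and not supported:

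- A reader might infer that the primary result is compromised. It is not, because FAS_ENR is defined consistently.
- A reader might infer that high-risk fetuses receive no efficacy analysis at all. If the PP text is taken literally they enter the pooled PP analyses, so what is missing is a dedicated one.
- A reader might want to put a size on the bias in the PP results. The documents give no expected share of high-risk fetuses in either arm, so no figure can be derived.

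**Conclusion.** The point holds as an internal contradiction in the SAP. By the plan's own definitions, four of the six subgroup tables contain none of the high-risk fetuses they are meant to describe. That conclusion needs no assumed rates. Separately, the Subgroup 3 description does not match the population it is said to equal, and this leaves at least one class of excluded fetus (isolated septal restriction) without a dedicated analysis. The per-protocol part is a gap in wording: the definitions omit an exclusion that the FAS definitions carry, and no text says that PP is a subset of FAS. The effect is confined to the descriptive high-risk analyses and the FAS–PP comparison. It should be settled before database lock, so that membership of these tables is not decided once outcomes are known.

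**What to change.** 1. In 4.6.3 and the table list, run the Subgroup 2 and 3 tables on the enrolled High-risk population of 2.1.5 and on its live-born part, and retitle the four tables. Add the High-risk population to the sets summarised in 4.2.
2. Reconcile the Subgroup 3 description with 2.1.5, so that every fetus excluded from the FAS appears in a dedicated table. State that the conditions are judged at inclusion. Widening Subgroup 3 to match 2.1.5 would move it away from the protocol's separate group and its subgroup c, both of which are built on severe MR with LA enlargement. The protocol wording must therefore be checked and aligned at the same time.
3. Define PP_ENR and PP_BIRTH as members of FAS_ENR and FAS_BIRTH without major protocol violations, keeping the intended-for-treatment condition for PP_BIRTH.

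The cost is SAP wording, table shells and a matching check of the protocol. No new data are needed, and the membership of FAS_ENR, the confirmatory tests and the stated power do not change.

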4.7 Safety Analyses

4.7.1 Fetal Left Heart Growth

Fetal left heart growth will be described longitudinally and analysed in exploratory manner as specified in the General Methodology above.

4.7.2 Intervention and Technical Details

Information about intervention and its technical details will be summarized on safety population per treatment groups.

Complications of fetal intervention and maternal complications 4.7.3

Data regarding complications and reasons for death will be described for safety population per treatment groups. No formal tests will be performed.

STATISTISKA KONSULTGRUPPEN	Statisti	cal Analysis Plan
Protocol: Effect of fetal aortic valvuloplasty on outcomes	Protocol No):
	Version: 1.0	Page 25 of 26

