1.2 Study Design

The study is an international multicenter prospective observational cohort study with a comparison cohort. Included are fetuses with a diagnosis of aortic stenosis who satisfy inclusion/exclusion criteria between 23+0 and 31+6 weeks of gestation. The decision whether a fetal balloon dilatation shall be attempted is not part of the study protocol. The number of examinations of mother/fetus/infant in this study is not different from the number of examinations that will be recommended for someone choosing not to be part of this study. The participation in the study is not affecting the treatment mothers and fetuses are receiving during pregnancy, nor how the infant is examined and treated after birth. The aim of the study is to, in a prospective and organized way, collect and evaluate multi-center data in order to reduce the risk for selection bias, missing data and inter-variability between participating centers.

Cases will be recruited from centers offering fetal aortic valvuloplasty and and from centers not offering this treatment. All intervention cases will be recruited from high volume

Protocol

Statistical Analysis Plan

Effect of fetal aortic valvuloplasty on outcomes

1.0

intervention centres which have performed at least 20 fetal cardiac interventions during the last five years before including the first case in the study. Fetal and postnatal echocardiographic examinations will be reviewed and remeasured by a core laboratory to confirm eligibility for inclusion, and identify potential measurement errors.

Data from two fetal echoes and one postnatal will be collected and each contains a comprehensive set of two-dimensional and Doppler measurements which will enable analysis of cardiac growth and development during pregnancy. Analysis of change of dimensions of the left heart structures and selected hemodynamic variables from the point of study inclusion until just before the first postnatal catheter or surgical procedure provides an opportunity to make a comparison between the groups that is unbiased with respect to centerspecific postnatal treatment policies. Three echocardiographic examinations and a 2-year follow-up regarding patient outcome will be performed as per Figures 1-3 below.

Figure 1. Study Overview – Fetal Protocol

STATISTISKA KONSULTGRUPPEN	Statistic	cal Analysis Plan
Effect of fetal aortic valvuloplasty on outcomes	Protocol No:	
	Version: 1.0	Page 8 of 26

Figure 2. Study Overview – Neonatal Protocol

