3.5.3 Fetal and maternal complications of fetal intervention

Safety of the prenatal procedure will be evaluated through the following variables:

- Intervention-related fetal death (defined as fetal death within 24 hours of procedure)
- Fetal death not directly related to the intervention, except termination of pregnancy
- Maternal complications to procedure (requiring intensive care or resulting in maternal death)
- Preterm delivery < 37 weeks
- Reasons for fetal or postnatal death

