4 STATISTICAL METHODOLOGY

4.1 General Methodology

Continuous variables will be described by means, standard deviation (SD), median and range, and categorical by number and percentages.

Main analyses will be performed comparing FAV 1+2 versus no-FAV 1+2 groups on FAS_{ENR} population. Complementary analyses will be performed on FAS_{BIRTH}, PP_{ENR} and PP_{BIRTH}. Separate descriptive comparisons between FAV 1 vs no-FAV 1 and FAV 1 vs no-FAV 1+2 groups will also be performed.

Comparisons between the two groups with respect to demographics and baseline characteristics and safety data will be performed using Fisher's exact test for dichotomous variables, Mantel-Haenszel Chi-square test for ordered categorical variables, Chi-square test for non-ordered categorical variables, and Fisher's non-parametric permutation test for continuous variables.

Due to the non-randomised design, all analyses will be adjusted for confounders. It is important that all known confounders at the time of inclusion are defined. The main confounders will be gestational age at first diagnosis and at inclusion, morphology and hemodynamics of the fetal heart at the time of study inclusion and possibly some data about the mother's health which could have an impact on the chance of success with fetal intervention, such as BMI. Although the study is designed to minimize bias by using strict echocardiographic inclusion criteria, it will be necessary to analyse the groups at baseline carefully with respect to a number of selected echocardiographic variables describing the size and function of the left heart. If this analysis shows that, in spite of the strict inclusion criteria, there are significant differences between the groups regarding data that are at the same time risk factors for the studied outcomes the analyses will be adjusted for those additionally defined confounders besides the known ones. A sensitivity analysis will also be performed for the primary variable applying propensity score matching procedure (1:1 or 2:1 if possible) including all variables that are of importance (p<0.10 using logistic regression) for discrimination of FAV vs no-FAV group and those identified/known confounders in the adjusted analyses.

Known confounders are:

• Gestational age at primary diagnosis (earlier gestational age could indicate more severe disease, and might differ between countries and centres due to different

Protocol

Statistical Analysis Plan

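### Crude fetal death percentages by arm in the safety tables ignore time at risk, so they are not comparable if the arms differ in gestational age at entry

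*SAP*

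**What the plan says.** **Entry.** SAP 1.2: "Included are fetuses with a diagnosis of aortic stenosis who satisfy inclusion/exclusion criteria between 23+0 and 31+6 weeks of gestation".

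**Safety variables.** SAP 3.5.3 lists, among others, "Fetal death not directly related to the intervention, except termination of pregnancy" and "Preterm delivery < 37 weeks". Neither is given a time origin, a denominator or a follow-up time. Procedure-related death is separate and has a fixed 24-hour window.

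**Safety analysis.** SAP 4.7.3: "Data regarding complications and reasons for death will be described for safety population per treatment groups. No formal tests will be performed". SAP 4.1 gives the form of description, continuous variables by the usual summaries "and categorical by number and percentages". Yet SAP 4.1 also plans tests: "Comparisons between the two groups with respect to demographics and baseline characteristics and safety data will be performed using" Fisher's exact test when the variable is dichotomous.

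**Confounding.** SAP 4.1 says in general terms that analyses will be confounder-adjusted. It names gestational age at diagnosis and at inclusion as known confounders and keeps only the more influential one if they are highly correlated. Of age at diagnosis it says: "earlier gestational age could indicate more severe disease, and might differ between countries and centres".

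**Related efficacy analysis.** SAP 3.4.2 has survival from fetal diagnosis to live birth as a time-to-event variable, with FAS_ENR as the main set. SAP 4.1 assigns it an adjusted Cox model. In the testing order of SAP 4.1 the third variable is worded as live birth at 37 weeks or later, which SAP 3.4.2 does not say.

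**The concern.** A fetus included at 24 weeks can be seen to die in utero over about 15 weeks; one included at 28 weeks, over about 11. Events before entry are never seen. If one arm enters earlier on average, its crude percentage of fetal deaths is higher even when the weekly risk is the same in both arms.

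A difference in entry age is plausible for three reasons.

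- Arm is tied to centre. Under SAP 1.4, no-FAV 1 comes only from centres that neither perform the procedure nor refer for it.
- SAP 4.1 expects age at diagnosis to vary between centres and to correlate with age at inclusion.
- FAV status requires the fetus to have survived until the needle is introduced (SAP 1.4). The FAV baseline echo is the last one before the intervention (Protocol, Electronic case report forms), so time zero can differ between arms.

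Non-procedural fetal death and preterm delivery are the listed fetal event rates that also exist in the comparison arm. Earlier FAV entry could make longer observation look like harm; later FAV entry could hide harm. The Protocol (Publication of results) allows safety to be reported in a paper of its own, before the primary outcome.

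**Working it through.** The plan states no fetal death rate, preterm rate or entry age by arm, so there is no figure of its own to reproduce here. All rates below are assumptions shown over a range. In every case the true treatment effect is zero.

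**1. Time at risk (entry limits from SAP 1.2)**

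- To an assumed birth at 39 weeks: 39 − 23 = 16.0 weeks for entry at 23+0, and 39 − 31.86 = 7.1 weeks for entry at 31+6. Ratio 2.2.
- To 37 weeks: 14.0 and 5.1 weeks. Ratio 2.7.

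**2. Fetal death, constant weekly hazard**

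Let R be the assumed risk over weeks 23-39. Then h = −ln(1 − R)/16, and the crude risk after entry at week e is 1 − exp(−h(39 − e)). For R = 10%, h = 0.10536/16 = 0.00659 per week. Entry at 24 weeks gives 1 − exp(−0.00659 × 15) = 9.4%; entry at 28 weeks gives 1 − exp(−0.00659 × 11) = 7.0%.

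| Assumed R | Entry 24 wk | Entry 28 wk | Ratio 24 v 28 | Difference, points | Ratio 26 v 28 | Ratio 23+0 v 31+6 |
|---|---|---|---|---|---|---|
| 3% | 2.8% | 2.1% | 1.36 | 0.7 | 1.18 | 2.22 |
| 5% | 4.7% | 3.5% | 1.35 | 1.2 | 1.18 | 2.21 |
| 10% | 9.4% | 7.0% | 1.35 | 2.4 | 1.17 | 2.18 |
| 15% | 14.1% | 10.6% | 1.34 | 3.6 | 1.17 | 2.14 |

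The ratio hardly depends on R; it follows the ratio of weeks observed (15/11 = 1.36). The last column would need every fetus in one arm to enter on the first eligible day and every fetus in the other on the last, so it is only an outer bound.

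**3. The same data per fetal-week**

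Expected fetal-weeks per fetus are (1 − exp(−hT))/h, with T the weeks from entry to birth. Deaths divided by fetal-weeks then equal h in both arms, a ratio of 1.00. This relies on a constant hazard. If the hazard changes with gestational age, the comparison needs risk sets on the gestational-age scale with delayed entry. With equal entry ages the crude ratio is also 1.00.

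**4. Preterm delivery**

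- (a) Constant hazard to 37 weeks, 10-30% risk over weeks 23-37: ratio 1.42 to 1.38 for 24 versus 28 weeks.
- (b) Risk q1 = 1-5% over weeks 23 to 32 and q2 = 10-25% from 32 to 36+6. Crude risk = 1 − (1 − q1)^((32 − e)/9) × (1 − q2). With q1 = 5% and q2 = 10%: 14.0% versus 12.0%, ratio 1.16. With q1 = 1% and q2 = 25%: 25.7% versus 25.3%, ratio 1.01.

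Every fetus enters before 32 weeks, so all share weeks 32 to 36+6, and only births before 32 weeks can differ through entry age. Model (a) treats a delivery at 25 weeks as likely, week for week, as one at 35, so (b) is the fairer guide.

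**5. Size against sampling error**

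Take 9.4% in 100 FAV and 7.0% in 50 no-FAV fetuses. The 95% half-width is 1.96 × √(0.0941 × 0.9059/100 + 0.0699 × 0.9301/50) = 9.1 points. The artefact of 2.4 points is 1.2 fetuses in an arm of 50.

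**The case against.** The case against has four parts.

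**The plan adjusts elsewhere.** SAP 4.1 announces adjustment generally, names age at inclusion as a confounder and gives logistic regression for dichotomous outcomes. A reader might therefore infer that these tables are adjusted. The specific text does not support that: SAP 4.7.3 is descriptive, the safety sentence in SAP 4.1 names an unadjusted test, and the table list marks Tables 2.1.x and 2.3.x as adjusted but not Table 3.2.1.

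**Fetal death also has a Cox model.** This stands in part, and it would be wrong to say that fetal death is reported only as a crude proportion. But that model has FAS_ENR as its main set, which leaves out the high-risk fetuses that SAP 2.1.1 expects to be overrepresented under FAV and that return in the safety population. Its clock starts at diagnosis, it states no delayed entry, and age at inclusion may be dropped for age at diagnosis. The term-birth wording of the third confirmatory test touches preterm delivery, but it conflicts with SAP 3.4.2 and cannot be relied on.

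**The bias is conditional and modest.** This stands. No entry age by arm is given, in size or direction, and the illustrated artefact is well inside sampling error.

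**It is partly visible already.** Gestational age at baseline echo and at birth is to be summarised by group (SAP 4.4), but for the FAS and PP sets, not for the safety population.

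**Conclusion.** The point holds as a gap in the safety reporting, mainly for non-procedural fetal death. If mean entry differs by two to four weeks, the crude percentages would show a ratio of about 1.17 to 1.35 with no true effect. This assumes a 3-15% fetal death risk over weeks 23-39, a constant hazard and birth at 39 weeks. For preterm delivery the ratio is probably 1.01 to 1.16 for a four-week gap. Procedure-related death within 24 hours is not affected.

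A reader might go further and infer that the earlier-enrolled arm must show more fetal deaths and preterm births by construction. The documents do not support that. It requires a difference in entry age, which they make plausible but do not state, and otherwise equal risks; case mix or a real treatment effect could outweigh it. Nor are these two events the only fetal safety variables with a comparator: left heart growth (SAP 3.5.1) is measured in both arms and modelled over time.

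The primary analysis is not touched. This is an inexpensive improvement to the secondary objective.

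**What to change.** In SAP 4.7.3 and Table 3.2.1, for the safety population and by arm:

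- Keep the crude counts and percentages.
- Add gestational age at entry, fetal-weeks at risk and the non-procedural fetal death rate per fetal-week.
- Add a descriptive cumulative incidence of fetal death with 95% CI on the gestational-age scale. Entry is delayed to inclusion, or to needle entry for FAV, so that weeks a FAV fetus survives by definition are not counted. Live birth is a competing event; state in advance whether termination of pregnancy competes or censors. Deaths within 24 hours of the procedure stay in their own row.
- Show delivery before 37 weeks the same way, as a supporting display.

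Also reconcile two pairs of statements: SAP 4.1 (Fisher's exact test for safety data) with SAP 4.7.3 (description only), and SAP 3.4.2 (live birth) with the third test in SAP 4.1 (live birth at term).

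The cost is SAP wording and one table. The eCRFs cover inclusion, fetal interventions, birth and subject termination, gestational age is calculated automatically, and the planned survival analysis already needs the event dates. The downside is wide intervals, especially at early gestational ages where few fetuses are at risk. The display corrects for time at risk only; it does not remove differences in case mix.
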